An investigator may discontinue or withdraw a participant from the study for the following reasons:

- Significant study SoA non-compliance
 - No phone call, text message or email responses per SOA or study coordinator inquiries
- If any clinical adverse event (AE), laboratory abnormality, or other medical condition or situation occurs such that continued participation in the study would not be in the best interest of the participant
- If the participant meets an exclusion criterion (either newly developed or not previously recognized) that precludes further study participation
- Participant unable to receive phone calls, text messages or email for 5 of the 10 days postoperatively.

The reason for participant discontinuation or withdrawal from the study will be recorded on the Case Report Form (CRF) by the local study team member. Subjects who sign the informed consent form and are randomized but do not receive the study intervention may be replaced. Subjects who sign the informed consent form, and are randomized and receive the study intervention, and subsequently withdraw, or are withdrawn or discontinued from the study, will not be replaced.

Section 8.10: Patient Replacement

Subjects who sign the informed consent form, and are randomized and receive the study intervention, and subsequently withdraw, or are withdrawn or discontinued from the study, will not be replaced.

Subjects who are found to be ineligible at any time prior to ureteral stent placement may be replaced.

Section 9: STUDY PROCEDURES

Time and Events Table

Procedures	Baseline Evaluation	Prior to operation	Operative Day	Ambulatory Assessments Days 1-10	Ambulatory Assessment Day 7 ²	Postoperative visit: Stent removal	Ambulatory Assessment Week 4 ³	Day ≤ 30	Day ≤ 60
Informed consent		X							
Study education		X							
Demographics	X								
Medical history	X								
Randomization			X						
Study intervention				X					
Radiologic imaging assessment ¹	X								
Daily EMA				X					
ROCKS PRO		X			X		X		
Follow-up assessments of study endpoints and safety								X	X
Complete Case Report Form (CRF)			X			X		X	X

¹: Urological imaging modality performed nearest to but prior to operative date.

²: Day 7 ambulatory assessment can be completed from post-operative day 7 through day 10.

³: Week 4 ambulatory assessment can be completed from post-operative day 22 through day 42.

Section 10: ADVERSE EVENTS

Section 10.1: Adverse Event Reporting Requirements

Adverse event (AE) monitoring and reporting is a routine part of every clinical trial and is done to ensure the safety of subjects enrolled in the studies as well as those who will enroll in future studies using similar agents. Data on adverse events will be collected from the time of the initial study intervention through 30 days after the study intervention. Any serious adverse event that occurs more than 30 days, and before 60 days of the study intervention and is considered related to the study intervention must also be reported. Serious Adverse Events (SAEs) will continue to be followed until:

- Resolution or the symptoms or signs that constitute the serious adverse event return to baseline;
- There is a satisfactory explanation other than the study intervention for the changes observed; or
- Death.

The investigator is responsible for the detection, documentation, grading, and assignment of attribution and expectedness of events meeting the criteria and definition of an AE or SAE. The definitions of AEs and SAEs are given below. It is the responsibility of the principal investigator to ensure that all staff involved in the trial is familiar with the content of this section.

Any medical condition or laboratory abnormality with an onset date before the initial study intervention will be considered pre-existing in nature. Any known pre-existing conditions that are ongoing at the time of study entry should be considered medical history.

For this study, non-serious AEs will not be reported to the IRB. SAEs will be reported in keeping with the governing IRBs guidelines.

Section 10.2: Definitions

1. Adverse Event

For the purposes of this trial, an adverse event (AE) is considered any untoward medical occurrence in a patient receiving study treatment that has or potentially has a causal relationship with this treatment. Any untoward medical occurrences that are unrelated to the study intervention will not be considered adverse events.

Symptoms of kidney stone disease and expected side effects from ureteroscopy lithotripsy and stent placement are not considered adverse events for this study. The following symptoms are indicative of underlying kidney stone disease and expected side effects from ureteroscopy with laser lithotripsy and stent placement, and will not be reported as adverse events (unless the event meets the criteria of an SAE):

- Hematuria
- Irritative voiding symptoms (e.g., urinary frequency, urgency, dysuria)
- Abdominal/flank/bladder pain
- Nausea and/or vomiting
- Dizziness and lightheadedness
- Urinary retention

Abnormal laboratory values or test results constitute adverse events only if they induce clinical signs or symptoms or require therapy. They are to be captured under the signs, symptoms, or diagnoses associated with them.

2. Serious Adverse Event

An adverse event is considered “serious” if, in the view of the investigator, it results in any of the following outcomes:

- Death
 - If death results from (progression of) the disease, the disease should be reported as an event (SAE) itself.
- A life-threatening adverse event

- An adverse event is considered 'life-threatening' if, in the view of either the investigator [or sponsor], its occurrence places the patient or subject at immediate risk of death. It does not include an adverse event that, had it occurred in a more severe form, might have caused death.
- Inpatient hospitalization or prolongation of existing hospitalization for > 24 hours.
- A persistent or significant incapacity or substantial disruption of the ability to conduct normal life functions
- A congenital anomaly/birth defect
- Important medical event
 - Any event that may not result in death, be life-threatening, or require hospitalization may be considered serious when, based upon appropriate medical judgment, they may jeopardize the patient and may require medical or surgical intervention to prevent one of the outcomes listed in this definition of "Serious Adverse Event". Examples of such medical events include allergic bronchospasm requiring intensive treatment in an emergency room or at home; convulsions that do not result in inpatient hospitalization or the development of drug dependency or drug abuse.

Hospital visits for conditions not associated with the urinary stone will not be collected or reported as SAEs.

3. Expected Adverse Event

An adverse event (AE) is considered "expected" if it meets the criteria of an AE per section 10.2, and is a known risk of general anesthesia and ureteroscopy such as:

- Myocardial infarction, deep vein thrombosis, cerebrovascular accident, pulmonary embolism, fever, UTI, sepsis, perinephric hematoma, acute kidney injury, ureteral injury or perforation, ureteral stricture or scarring, stent migration or dislodgement, stent encrustation

4. Unexpected Adverse Event

An adverse event (AE) is considered "unexpected" if it meets the criteria of an AE per section 10.2, and is not expected as described above.

Section 10.3: Reporting of Unanticipated Problems

Upon becoming aware of any incident, experience, or outcome (not related to an adverse event) that may represent an unanticipated problem, the investigator should assess whether the incident, experience, or outcome represents an unanticipated problem. The incident, experience or outcomes is considered unanticipated if it meets all of the following criteria:

1. Unexpected (in terms of nature, severity, or frequency);
2. Related or possibly related to participation in the research; and
3. Suggests that the research places subjects or others at a greater risk of harm than was previously known or recognized.

If the investigator determines that the incident, experience, or outcome represents an unanticipated problem, the investigator must report it to the IRB according to the local IRB policies.

Section 10.4: Unblinding Procedures

To minimize bias in patient-reported outcome measures, all reasonable efforts will be made to keep patients blinded to their randomized treatment allocation. This will help to assure that all patient-reported outcomes and clinical data collection for the trial have been completed prior to unblinding. Patients will be notified of their randomized treatment allocation by trial staff at the coordinating center at the conclusion of the study.

In the case of a medical emergency or other event in which the participant's knowledge of their treatment allocation is critical to the participant's clinical management, the blinding for that participant may be broken by the investigator. The investigator or their designee must document the date and reasons for such emergency unblinding in the participant's source documents. The investigator must also immediately notify the study PI and trial coordinating center of such an event.

Section 10.5: Stopping Rules

An interim analysis for futility is planned after accrual of 112 patients. The study will stop early if it is found that the silicone stent arm has clinically significant worse pain intensity and worse pain interference at 7 days with worse pain defined as 5 or greater t-score points worse pain in the silicone stent arm compared to the non-silicone stent arm after adjusting for baseline. Under the alternative hypothesis for both endpoints simulations of 1000 trials estimates the probability of stopping early is 0%. If we assume that the silicone stent is worse than the non-silicone stent by 5 points simulation of 1000 trials estimates the probability of stopping early is 24.4%.

Section 11: STATISTICAL CONSIDERATIONS

Section 11.1: Statistical Hypotheses

This is a multi-center two-arm stratified, randomized comparative effectiveness study in patients are treated with URS for nephrolithiasis with a planned placement of a stent to assess patient reported quality of life. The primary hypothesis is that the silicone ureteral stent arm will have superior patient reported pain outcomes compared to the non-silicone stent arm. Patients will be stratified by stone location (kidney only / ureteral) and randomized to receive a silicone stent or a non-silicone stent and complete the PROMIS® pain intensity and PROMIS® pain interference surveys prior to surgery and at 7 days after stent placement.

Our formal statistical hypotheses are:

$$H_0: \mu_{ns} = \mu_{ss}, \quad H_1: \mu_{ns} \neq \mu_{ss}$$

where, μ_{ns} = mean PROMIS® pain intensity in non-silicone stent arm at 7 days

μ_{ss} = mean PROMIS® pain intensity in silicone stent arm at 7 days

AND

$$H_0: w_{ns} = w_{ss} \quad H_1: w_{ns} \neq w_{ss}$$

where, w_{ns} = mean PROMIS® pain interference in non-silicone stent arm at 7 days

w_{ss} = mean PROMIS® pain interference in silicone stent arm at 7 days

Section 11.2: Power/Sample Size:

Assume that the correlation of baseline is 0 for purposes of the sample size calculation. If this assumption is violated, the power for each hypothesis will be greater than the stated power.

A clinically meaningful change in pain PROMIS® score is between 4 and 6 and the standard deviation of the score is 10(16-18). Assuming a 5 t-score PROMIS® pain point difference between 2 arms and a standard deviation of 10, a t-test including 101 patients per arm has 90% power with a 2-sided alpha = 0.025. Assuming a 10% loss-to-follow-up, accrual of 224 study treated patients (112 patients per arm) is planned. Our planned analysis does not match this calculation because we will adjust for the baseline pain to ensure any imbalance prior to surgery is accounted for. However, this power calculation, by ignoring the adjustment of baseline pain, is accurate if the correlation of baseline pain with our outcome is 0. If the correlation is greater than 0, then we will have more power than described.(19)

Section 11.3: Populations for Analyses

Modified Intent-to-Treat (m-ITT) Population: All participants eligible and randomized who complete the pain intensity and pain interference questionnaire between 7-10 days post-URS will be included.

Subjects will be analyzed by assigned treatment at randomization. This is the main population for efficacy analyses.

Per-Protocol Population: All Patients eligible and randomized patients who complete the pain intensity and pain interference questionnaire between at 7 days post-URS will be included per treatment arm received. This second population will be used to assess the robustness of the primary and secondary efficacy outcomes.

Safety Population: All patients who are randomized and receive a stent will be define the safety population and used for all safety analyses. Subjects will be analyzed by assigned treatment arm.

Section 11.4: Statistical Analyses

General Approach

Descriptive statistics for the study population will be reported using frequentist statistics. In general, continuous measures will be reported using means and standard deviations or medians and the interquartile range as the distribution warrants. Categorical variables will be reported as counts and proportions.

Analysis of the Primary Efficacy Endpoints

The primary endpoints of the study are PROMIS® pain intensity and PROMIS® pain interference t-scores. Each endpoint will be analyzed separately using an ANCOVA model for each. Using the MITT population for analysis, the t-score of the PROMIS® outcome at 7 days post-URS will be the dependent variable and treatment arm and pre-treatment (baseline) PROMIS t-score will be independent variables. The primary comparison of interest is treatment arm. The baseline adjusted mean pain score at 7-days will be reported by arm with the 97.5% confidence interval and a type-3 F-test will test the hypothesis that pain differs between the two treatment groups. Each endpoint modeled will test the effect of treatment arm adjusting for baseline with a type I error of 2.5% for an overall study type I error of 5%.

An analysis in the per-protocol population will be assess the robustness of the effect found in the primary analysis. Additionally, a multivariable model will be considered to account for other patient or surgical variables that may be unbalanced between the arms including timing of stent removal or stone location.

Analysis of the Secondary Endpoints

Additional health-related quality of life endpoints including PROMIS® Pain scores at 4 weeks will be analyzed with similar models described for the primary endpoint. A linear mixed model will be used to compare LURN SI-10 scores at 7 days and 4 weeks between treatment arms. Each analysis will report means with 95% confidence intervals at each time for each arm with a model based type-3 F-test comparing treatment arms.

Healthcare utilization within 30 days of URS will be assessed using a composite endpoint. The composite healthcare utilization metric within 30 days will be a composed score based upon utilization by the patient with each patient assigned a score based upon the highest utilization level that they participate in with levels defined in decreasing order:

5. Hospitalization and ICU care
4. Unplanned hospitalization
3. Emergency department visit
2. Ambulatory encounter: Clinic visit
1. Ambulatory encounter: Phone call or message

We will compare the composite score ranking between the treatment arms using a WinRatio analysis using the unmatched approach.(20) The median composite score for each arm will be reported, along with the WinRatio and associated 95% confidence interval and p-value.

Abnormal imaging and stone-free rates will each be summarized as a count with the associated proportion by treatment arm and tested with a chi-square test (or fisher's exact test if event counts are 5 or less.)

Planned Interim Analyses

An interim analysis for futility is planned after accrual of 112 patients. The study will stop early if it is found that the silicon stent arm has clinically significant worse pain intensity and worse pain interference at 7 days with worse pain defined as 5 or greater t-score points worse pain in the silicone stent arm compared to the non-silicone stent arm after adjusting for baseline. Under the alternative hypothesis for both endpoints simulations of 1000 trials estimatas the probability of stopping early is 0%. If we assume that

the silicone stent is worse than the non-silicone stent by 5 points simulation of 1000 trials estimates the probability of stopping early is 24.4%.

Sub-Group Analyses

A sub-group analysis by stone location is planned. Primary and secondary endpoints will be reported for ureteral stones separately from renal stones.

Exploratory Analyses.

The mean (with standard deviation) or median (with interquartile range) days taken off work by patient and separately by caregiver will be compared between treatment arms with a t-test or Wilcoxon rank test if the distribution warrants.

Ecological Momentary Assessments of pain and PROMIS® daily ability to participate in social roles and activities score measured via daily text message will be displayed using spaghetti plots. Each measure will be analyzed with a linear mixed model including fixed effects of treatment arm, day, and the interaction of treatment arm and day. As this is an exploratory endpoint, these models will be explored using several methods to address missing data and model fit.

Each healthcare utilization metric within 30 days of URS will be summarized separately as a count with the associated proportion by treatment arm and tested with a chi-square test (or Fisher's exact test if event counts are 5 or less.)

In an exploratory analysis to create a composite endpoint to be used in future trials we will assess the plausibility of 2 composite measurement plans and analyses of these.

In addition to the WinRatio, our second composite analysis will include healthcare utilization and PROMIS® Pain. Additionally, we will use a composite score ranking of healthcare utilization similar to the WinRatio plan and add the PROMIS® Pain scores to the analysis using DOOR. The probability that a randomly selected patient will have a better DOOR if assigned to the silicone stent will be estimated.(21) The WinRatio and DOOR composite healthcare utilization metric ratios' sizes and directions will be compared.

The number and proportion of patients who are prescribed opioid medications will be reported by arm and compared using a chi-square test.

Satisfaction score assessed using the ICIQ-S will be summarized at 7 days and 4 weeks by arm with means and standard deviations. A repeated measures model will be used to test if satisfaction differed at either time between treatment arms using an interaction of time and arm.

Section 12: DATA AND SAFETY MONITORING

The DSMC will consist of the MUSIC ROCKS Program Manager, Program Director, Statistician, and other members of the MUSIC ROCKS team. This committee is responsible for monitoring the safety and data integrity of the study.

Each performance site's local study team is required to meet virtually with the DSMC and BLUES study team every six months if it is determined by the DSMC and/or Principal Investigator that a virtual meeting is necessary. The discussion may include matters related to the safety of study participants (Serious Adverse Event, Adverse Event and Unanticipated Problem reporting), completeness, validity and integrity of the study data, enrollment rate relative to expectations, characteristics of participants, retention of study participants, and adherence to the protocol (potential or real protocol deviations). If there are no concerns around any of the aforementioned items, the principal investigator and/or the DSMC may decide that a meeting is unnecessary and if so, a progress summary communication will serve in its place. Additionally, a member of the BLUES study team will send a communication summarizing current progress to each site on a monthly basis. These communications will consist of 1) any identified Serious Adverse Events and necessary follow-up, 2) enrollment rate relative to expectations, and 3) any identified protocol deviations, unanticipated problems, and recommendations to prevent additional instances.

These 6-month meetings are to be documented by the BLUES study coordinator or the BLUES trial project manager and will include the topics listed above as appropriate. The meeting minutes must be signed by the Principal Investigator or by one of the co-investigators.

The BLUES study team is responsible for collating all the meeting documentation for participating sites and will report any serious adverse events, unanticipated problems, and protocol deviations as outlined in section 10.

Section 13: QUALITY ASSURANCE AND AUDITS

The Data and Safety Monitoring Committee can request a 'for cause' quality assurance audit of the study if the committee identifies a need for a more rigorous evaluation of study-related issues.

A regulatory authority (e.g. FDA) may also wish to conduct an inspection of the study, during its conduct or even after its completion. If an inspection has been requested by a regulatory authority, the site investigator must immediately inform the BLUES study team that such a request has been made.

Section 14: CLINICAL MONITORING PROCEDURES

Prior to subject recruitment, a participating site will undergo site initiation meeting to be conducted by the BLUES study team. This will be done as a teleconference, videoconference, or web-based meeting after the site has been given access to the study database, provided the BLUES study team the necessary regulatory documentation and received IRB approval. The site's principal investigator and study staff should make every effort in attending the site initiation meeting. Study-related questions or issues identified during the site initiation meeting will be followed-up by the appropriate BLUES study team personnel until they have been answered and resolved.

Monitoring of this study will include centralized surveillance of study specific MUSIC registry data by the BLUES study team to confirm adherence to the protocol. The BLUES study team will meet at least once per month to review findings of surveillance and may engage sites ad-hoc as appropriate. Additional monitoring will be performed by the BLUES study staff members on an annual basis.

REFERENCES

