Immediate. Based upon prior RCT outside of the United States, the use of silicone ureteral stents has the potential to decrease pain and LUTS after URS.(12) Decreased pain and LUTS after URS secondarily could decrease the rate of ambulatory healthcare utilization, opioid prescriptions, postoperative ED visits, and unplanned hospitalizations. It could also decrease the number of days required to miss work due to recovery.

Long-range. Decreased pain and LUTS after URS secondarily could decrease a patient's exposure to opioid analgesia postoperatively. Less patient requirements for opioid analgesia could decrease the incidence of new persistent long-term use of opiates in these patients.

Section 5: STUDY OBJECTIVES**Section 5.1: Primary Objectives**

1. To determine the health-related quality of life and symptoms in patients with urinary stone disease stented with silicone or polyurethane stents at ureteroscopy.

Section 5.2: Secondary Objectives

1. To compare 30-day emergency department visits and hospitalization rates between study arms
2. To compare rates and intensity of ambulatory healthcare encounters after ureteroscopy and stenting between study arms
3. To compare stone-free rates between study arms
4. To compare abnormal imaging findings after ureteroscopy and stenting between study arms

Section 5.3: Exploratory Objectives

1. To compare days taken off work by patient between study arms
2. To compare days taken off work by caregiver between study arms
3. To compare Ecological Momentary Assessments (EMA) measured via daily text message for 10 days between study arms
4. To compare Composite score difference between Winratio and Desirability Of Outcome Ranking (DOOR) between study arms
5. To compare number of patients receiving opioid prescriptions between study arms
6. To compare ICIQ-s score at 7 days between study arms
7. To compare ICIQ-s score at 4 weeks between study arms

Section 5.4: Endpoints

- Primary Efficacy Endpoint(s):
 - Silicone stent placement will be associated with significantly improved PROMIS® scores of pain intensity and interference at 7 days compared to non-silicone stent placement.
- Secondary Efficacy Endpoint(s):
 - Silicone stent placement will be associated with equivalent PROMIS® scores of pain intensity and interference at 4 weeks compared to non-silicone stent placement.

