 - Silicone stent placement will be associated with significantly improved NIH LURN SI-10 scores from baseline at 7 days compared to non-silicone stent placement.

- Silicone stent placement will be associated with equivalent difference in NIH LURN SI-10 scores from baseline at 4 weeks compared to non-silicone stent placement.
- Silicone stent placement will be associated with improved composite healthcare utilization metric within 30 days compared to non-silicone stent placement.
 - Hospitalization and ICU care
 - Unplanned hospitalization
 - Emergency department visit
 - Ambulatory encounter: Clinic visit
 - Ambulatory encounter: Phone call or EMR message
- Silicone stent placement will be associated with equivalent abnormal imaging findings within 60 days compared to non-silicone stent placement.
 - New/worsening hydronephrosis
- Silicone stent placement will be associated with equivalent stone-free rates within 60 days compared to non-silicone stent placement.
- Tertiary/Exploratory Endpoint(s):
 - Silicone stent placement will be associated with significantly improved Ecological Momentary Assessment (EMA) scores measured via daily text message for 10 days compared to non-silicone stent placement.
 - Daily visual analog scale survey for pain
 - PROMIS® daily ability to participate in social roles and activities score
 - Silicone stent placement will be associated with significantly less number of days taken off work by patient.
 - Silicone stent placement will be associated with significantly less number of days taken off work by caregiver.
 - Silicone stent placement will be associated with significantly improved composite healthcare utilization metric within 30 days compared to non-silicone stent placement using Desirability of Outcome Rating (DOOR) method
 - The WinRatio and DOOR composite healthcare utilization metric ratios' sizes and directions will be compared.
 - Silicone stent placement will be associated with significantly less number of opioid prescriptions received.
 - Silicone stent placement will be associated with significantly improved ICIQ-S scores at 7 days compared to non-silicone stent placement.
 - Silicone stent placement will be associated with significantly improved ICIQ-S scores at 4 weeks compared to non-silicone stent placement.

Section 6: PATIENT ELIGIBILITY

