The patient's post-operative care will proceed per standard of care, and their follow up, imaging and clinic visits will be directed by the local surgeon according to their local protocol. All patients will be provided with the MUSIC pain optimization pathway (POP) medication for post-operative symptoms for ureteroscopy. The standard within MUSIC is to prescribe non-steroidal anti-inflammatory drugs (NSAIDs), alpha-blockers and an anti-cholinergic as first line therapy. Opiate pain medication is not recommended as first line therapy. Patients will also be provided the MUSIC pain management and stent specific education brochures.

The BLUES study is pragmatic. Stents will be removed at a time and duration per the surgeon's discretion. The patient's information regarding post-operative course will be collected into the registry 60 days after the surgery, keeping with current practice for MUSIC ROCKS patient registry entry.

Specific assessments obtained on the postoperative day 1 through 10, include:

- ROCKS PRO day 7 questionnaire
 - Participants will complete their day 7 ROCKS PRO questionnaire, consisting of PROMIS® scores of pain intensity and interference, LURN SI-10 score Baseline ICIQ-S score, stent specific USSQ question and reported number of days off work (Figure 1)
- Ecological Momentary Assessment (EMA) measured via daily text message
 - Participants will complete a single visual analog scale survey for pain and one functional ability question from the PROMIS® ability to participate in social roles and activities (Figure 2)

Specific assessments obtained on the postoperative day ≤ 60, include:

- ROCKS PRO 4-week questionnaire

- Participants will complete their 4-week postoperative ROCKS PRO questionnaire, consisting of PROMIS® scores of pain intensity and interference, LURN SI-10 score Baseline ICIQ-S score, stent specific USSQ question (Figure 1)
- Stone-free rates within 60 days
 - Participants after URS are often requested to obtain renal imaging within 8 weeks. However, since this is a pragmatic study, patients are asked to receive imaging based on provider discretion, and some patients do not attend their imaging appointment, Utilizing MUSIC and ROCKS existing infrastructure. Stone free defined as no residual fragments identified on any postoperative imaging (ultrasound, abdominal X-ray, CT or any combination) within 60 days

Section 8.4: Concomitant Medications/Treatments

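### Four secondary endpoint statements in Section 5.4 are worded as equivalence, but Section 11.4 plans only tests of difference, with no designated margin and no between-arm confidence interval for them

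*Combined protocol and SAP*

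**What the plan says.** Section 5.4 (Endpoints) lists secondary efficacy statements of two kinds. Some predict improvement, for example 7-day LURN SI-10 and the 30-day utilization composite. Four predict equivalence:

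- 4-week PROMIS pain, which covers two scores: "Silicone stent placement will be associated with equivalent PROMIS® scores of pain intensity and interference at 4 weeks"
- 4-week LURN SI-10: "equivalent difference in NIH LURN SI-10 scores from baseline at 4 weeks"
- abnormal imaging: "Silicone stent placement will be associated with equivalent abnormal imaging findings within 60 days"
- stone-free rate: "Silicone stent placement will be associated with equivalent stone-free rates within 60 days compared to non-silicone stent placement"

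Elsewhere the wording is softer. Section 5.2 (Secondary Objectives) says "To compare stone-free rates between study arms" and treats abnormal imaging the same way. The endpoint list in the synopsis is neutral.

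Section 11.4 (Analysis of the Secondary Endpoints) plans models like the primary ANCOVA for 4-week PROMIS and a linear mixed model for LURN SI-10. Both report a mean with 95% CI for each arm and a type-3 F-test between arms. Abnormal imaging and stone-free rate are reported as counts and proportions by arm, with a chi-square or Fisher test.

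On follow-up imaging, Section 8.3 says that "patients are asked to receive imaging based on provider discretion, and some patients do not attend their imaging appointment".

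**The concern.** A test of no difference can reject equality. Failing to reject it does not show that the arms are close. To support equivalence, a plan needs a margin fixed in advance and an interval for the between-arm difference to set against it. Section 11.4 supplies neither for these four statements, and it analyses statements of improvement and statements of equivalence in the same way. LURN SI-10 at 7 days (improved) and at 4 weeks (equivalent) even share one model and one kind of test.

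What is at stake is the wording of secondary conclusions. Stone-free rate and new or worsening hydronephrosis are where readers will look for reassurance that a possibly more comfortable stent gives nothing up. As written, the plan offers a p-value that cannot give that reassurance.

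**Working it through.** **1. Statement against analysis**

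| Statement (Section 5.4) | Planned test (Section 11.4) | Planned interval | Margin |
|---|---|---|---|
| PROMIS intensity and interference, 4 weeks | F-test of difference | per-arm 95% CI | none designated |
| LURN SI-10, 4 weeks | F-test of difference | per-arm 95% CI | none |
| Abnormal imaging, 60 days | chi-square or Fisher | none | none |
| Stone-free rate, 60 days | chi-square or Fisher | none | none |

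The only between-arm interval among the secondary analyses is the 95% CI for the WinRatio. It belongs to the utilization composite, which is worded as improved.

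**2. Figures that could serve as a margin**

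For PROMIS, Section 11.2 says "A clinically meaningful change in pain PROMIS® score is between 4 and 6" and sizes the trial on 5 points. The interim rule in Sections 10.5 and 11.4 also uses 5 points. None of these is designated as an equivalence margin. For LURN SI-10, abnormal imaging and stone-free rate the documents give no figure at all.

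**3. The plan's own sample size**

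Section 11.2: "a t-test including 101 patients per arm has 90% power with a 2-sided alpha = 0.025", for 5 points and SD 10. The t-test calculation gives 100.6, so 101 per arm, with power 90.1%. The figure reproduces. It sizes the primary superiority test; no power is stated for the equivalence statements.

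**4. How often a real stone-free difference would be non-significant**

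Assumptions, none of them in the documents: true rates 80% and 70%; 112 per arm imaged (everyone) or 70.

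Normal approximation: P(non-significant) = Phi((1.96 x s0 - 0.10)/s1), where s0 = sqrt(2 x 0.75 x 0.25/n) and s1 = sqrt((0.8 x 0.2 + 0.7 x 0.3)/n).

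- n = 112: s0 = 0.0579, s1 = 0.0575; Phi(0.233) = 0.592
- n = 70: s0 = 0.0732, s1 = 0.0727; Phi(0.598) = 0.725

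Exact enumeration of all pairs of binomial counts, with Fisher when any cell is 5 or less and uncorrected chi-square otherwise, gives 0.590 and 0.720.

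Other assumed pairs by the same enumeration, at 112 and 70 per arm: 90% vs 80% gives 0.433 and 0.646; 70% vs 60% gives 0.650 and 0.764. If both rates are truly 80%, the result is 0.95 at both sizes, so the dependence on numbers imaged arises only when a true difference exists.

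**5. Power if a PROMIS margin were set**

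SD 10 (Section 11.2), zero true difference, no gain from baseline adjustment, equivalence concluded if the 90% CI lies within the margin. SE = 10 x sqrt(2/n): 1.407 at 101 per arm and 1.581 at 80 (the 80 is an assumption). Power per score = 2 x Phi(margin/SE - 1.645) - 1.

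| Margin | 101 per arm | 80 per arm |
|---|---|---|
| +/-4 | 2 x Phi(1.198) - 1 = 77% | 2 x Phi(0.885) - 1 = 62% |
| +/-5 | 2 x Phi(1.908) - 1 = 94% | 2 x Phi(1.517) - 1 = 87% |

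For both scores jointly at 101 per arm, if the two estimates correlate 0.5 to 0.9 (assumed), power is about 62-70% at +/-4 and 90-92% at +/-5.

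**The case against.** The best counter-argument is that the word is loose. The statements sit under an endpoints heading. Section 11.1 reserves formal hypotheses for the two 7-day PROMIS scores, Section 5.2 speaks only of comparing imaging and stone-free rates, and the synopsis is neutral. Read this way, the authors expect benefit around day 7 and no difference later, and Section 11.4 duly compares. This softens the point but does not remove it. Section 5.4 sets the word beside others that predict improvement, and if it is loose, correcting it is easy.

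A second objection is that the missing interval is partly presentational. The ANCOVA and mixed models estimate the arm contrast, and a difference in proportions follows from the counts. That is fair: the information will exist. It is simply not listed for reporting, and no margin is designated to judge it by.

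Two stronger readings are tempting, and the documents support neither.

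- A reader might infer that the sponsor intends to report a non-significant p-value as equivalence. No section says so.
- A reader might infer that there is nothing to judge any of these differences against, or that the trial is too small for any equivalence conclusion. For PROMIS that is wrong: the protocol gives 4-6 points and uses 5, and a +/-5 margin would have 94% power per score at 101 per arm. It is true only of the other three endpoints that no figure is given.

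**Conclusion.** The point holds as a minor one. The four equivalence statements cannot be supported by the planned tests, because no margin is designated and no between-arm interval is listed for them.

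The text comparison needs no assumptions. The illustration does: 59% and 72% non-significant rest on assumed rates of 80% and 70% and on 112 or 70 imaged per arm. Across the three assumed 10-point differences the range is 43-65% at 112 and 65-76% at 70. The PROMIS power figures rest on the protocol's SD of 10, zero true difference and no baseline gain, and they depend strongly on whether 4 or 5 points is chosen.

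The primary endpoints, their analysis and the sample size are unaffected.

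**What to change.** 1. In Section 5.4, replace the equivalence wording in all four statements with *no difference is expected*.
2. In Section 11.4, add for each of these endpoints the between-arm difference with its 95% CI (baseline-adjusted for PROMIS).
3. State that a non-significant test will not be reported as equivalence.
4. Optional, for 4-week PROMIS only: pre-specify a margin justified from the protocol's own figures, conclude equivalence only if the 90% CI of the baseline-adjusted difference lies within it, and state the power for one score and for both.

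The cost is a few sentences and one interval per comparison, made before results are known. No patients or data are added. The downside is giving up an equivalence statement for LURN SI-10, abnormal imaging and stone-free rate, and, if the PROMIS option is taken at +/-4, accepting limited power.
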